17.1.2. ANNUALIZED CHANGE IN CKD-EPI eGFR

The CKD-EPI values will be computed for every visit using the following equation: (Levey et.al.,2009):

$$\text{CKD-EPI eGFR} = 141 \times \min(\text{SCR}/k, 1)^{\alpha} \times \max(\text{SCR}/k, 1)^{-1.209} \times 0.993^{\text{Age}} \times 1.018(\text{if female}) \times 1.159(\text{if black})$$

where

Document: \\quintiles.net\enterprise\Sites\CAMTL\IntProjects\SasData\Amicus\AT1001\AXA23225A\Biostatistics\Documentation\SAP\DR\Amicus_AT1001-042_SAP_Final_v1.0_20190821.docx

Author:	Amicus	Version Number:	Final v1.0
		Version Date:	21AUG2019

Template No.: CS_TP_BS016 Revision 5

Reference: CS_WI_BS005

Effective Date: 01Apr2018

17.1.6. ECHOCARDIOGRAPHY (ECHO)

An ECHO will be performed at baseline, and every 12 months subsequently until the end of study visit, and the ECHO data will be collected in the EC domain. The following parameters will be summarized separately in tables

- LVM and LVMi
- Ejection Fraction
- Fractional Shortening
- LVIDd, LVIDs, MWFS, Wall Thickness.

These parameters will be presented to summarize the data by each visit for baseline, post-baseline and change from baseline. Supportive listings to these parameters will also be provided. ECHO parameters for safety evaluation is provided in the Safety Outcomes section.

17.1.7. SF-36 QUESTIONNAIRE

SF-36 is an indicator of overall health status which consists of eight sub-scaled scores. The scores are weighted sums of the questions in each sub-scale. The SF-36 will be collected at Baseline, and every 6 months subsequently until the End of Study visit. The SF-36 consists of the following subscales:

- Physical Functioning (PF)
- Role Physical (RP)
- Bodily Pain (BP)
- General Health (GH)
- Vitality (VI)
- Social Functioning (SF)
- Role Emotional (RE)
- Mental Health (MH)

And can be further summarized into physical and mental components:

- Physical Component Summary
- Mental Component Summary

Norm based scoring of the SF-36v2 will be performed by OPTUM Insight Life Sciences and the above mentioned sub-scales and component summaries will be provided. Each sub-scale and component summary scores will be summarized at baseline and every post-baseline visit, as well as change from baseline, in a summary table.

Document: \\quintiles.net\enterprise\Sites\CAMTL\IntProjects\SasData\Amicus\AT1001\AXA23225A\Biostatistics\Documentation\SAP\DR\Amicus_AT1001-042_SAP_Final_v1.0_20190821.docx

Author: Amicus

Version Number: Final v1.0

Version Date: 21AUG2019

Template No.: CS_TP_BS016 Revision 5

Reference: CS_WI_BS005

Effective Date: 01Apr2018

Three listings presenting SF-36 individual questions, norm based scores, and physical and mental component summary scores will be provided.

18. SAFETY OUTCOMES

The safety parameters include Adverse Events, Physical Examination, Vital Signs, Laboratory Tests, 12 Lead ECG, use of Concomitant Medications. All outputs for safety outcomes will be based on the ITT population using nominal visits (not including unscheduled visits and early termination) except tables presenting clinically significant results. These tables presenting clinically significant results will include unscheduled visits and early termination alongside the scheduled visits. Each continuous variable will be summarized for quantitative analysis using descriptive statistics by each visit including baseline, and change from baseline for that visit. Categorical variables will be summarized for qualitative analysis using incidence counts and percentages. The summary will be performed by each visit including baseline for each categorical parameter (e.g. Urinalysis parameters except pH and specific gravity).

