7.3. RETESTS, UNSCHEDULED VISITS AND EARLY TERMINATION DATA

In general, for by-visit summaries, data recorded at the nominal visit will be presented. Unscheduled measurements will not be included in by-visit summaries but will be included in tables presenting the clinically significant (CS) evaluations at any time of the study. All visits, including nominal, unscheduled, retest, and early termination visits will be sorted and presented chronologically. The visit wording to be presented in all outputs can be referred in Appendix 1.

In the case of a retest (same visit number assigned but tested on different dates), the first available measurement for that visit will be used for by-visit summaries.

Listings will include scheduled, unscheduled, retest and early discontinuation data.

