Quantitative laboratory measurements reported as “< X”, e.g. below the lower limit of quantification (BLQ), or “> X”, e.g. above the upper limit of quantification (ULQ), will be converted to X for the purpose of quantitative summaries, but will be presented as recorded, e.g. as “< X” or “> X” in the listings.

Listings presenting lab results in each subcategory (e.g. Hematology, Serum Chemistry, Urinalysis, 24-hour Urine, Serum Pregnancy, and Urine Pregnancy) will be provided.

A listing of subjects with at least one assessment falling outside of the normal range will also be provided and clinical significance will be included in this listing.

A listing including all historical laboratory data will be provided.

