18.4.1. LABORATORY REFERENCE RANGES AND CLINICAL SIGNIFICANCE

Quantitative laboratory measurements will be compared with the relevant laboratory reference ranges in SI units and categorized as:

- Low: Below the lower limit of the laboratory reference range.
- Normal: Within the laboratory reference range (upper and lower limit included).
- High: Above the upper limit of the laboratory reference range.

For reference range with a single boundary, there will be only two of the three categories presented for the parameter (either Low/Normal, or Normal/High), e.g. Magnesium concentration is deemed High if result > 1.25 mmol/L, and Normal if at or below 1.25 mmol/L.

For categorical results in Urinalysis, they will be categorized into two categories, i.e. Normal/Abnormal if the result is different from that of the normal reference value. Shifts from baseline to any post-baseline visit summary tables based on the Low/Normal/High categories (and the variants) described above will be provided.

In addition to the high and low quantitative laboratory assignments, any result deemed clinically significant by the PI will be captured in the eCRF, and will be presented in the summary tables.

Document: \\quintiles.net\enterprise\Sites\CAMTL\IntProjects\SasData\Amicus\AT1001\AXA23225A\Biostatistics\Documentation\SAP\DR\Amicus_AT1001-042_SAP_Final_v1.0_20190821.docx

Author: Amicus

Version Number: Final v1.0

Version Date: 21AUG2019

Template No.: CS_TP_BS016 Revision 5

Reference: CS_WI_BS005

Effective Date: 01Apr2018

18.5. 12 LEAD ECG (ECG) EVALUATIONS

Results from the central ECG (Electrocardiogram) Reading Centre will be included in the reporting of this study. The following ECG parameters will be reported in summary tables using descriptive statistics for this study:

- PR Interval (msec)
- QRS Interval (msec)
- QT Interval (msec)
- QTcF Interval (msec)
- HR (bpm)
- RR (msec)

All findings, including clinically significant findings, will be captured by the eCRF for the overall ECG evaluation, and categorized into Normal; Abnormal, NCS; and Abnormal, CS.

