In addition to the change from baseline descriptive statistics summary, the number and percentage of subjects will be presented in a table for the overall ECG evaluation of clinical significance at any time of the study including unscheduled visits. A shift table by visits will also be constructed for change from baseline to post-baseline visits with regards to the three categories of the overall ECG evaluation.

A listing presenting all available ECG assessments will be provided. In addition, a listing of subjects with at least one clinically significant finding will be provided.

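### Lab shift tables use nominal visits only, so liver and creatinine values from between visits reach a lab summary table only on the investigator's judgement, and the visible SAP has no count against the protocol's lab thresholds

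*SAP*

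**What the plan says.** **The general rule.** SAP 18 bases safety outputs on nominal visits: they are "based on the ITT population using nominal visits (not including unscheduled visits and early termination) except tables presenting clinically significant results". SAP 7.3 keeps unscheduled values out of by-visit summaries. Where one visit number has tests on different dates, "the first available measurement for that visit will be used for by-visit summaries".

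**Labs.** SAP 18.4.1 promises "Shifts from baseline to any post-baseline visit summary tables based on the Low/Normal/High categories" and does not mention unscheduled values. It adds that "any result deemed clinically significant by the PI will be captured in the eCRF, and will be presented in the summary tables". Under SAP 7.3, unscheduled measurements "will be included in tables presenting the clinically significant (CS) evaluations at any time of the study". Listings carry everything, and SAP 18.4 says "A listing of subjects with at least one assessment falling outside of the normal range will also be provided".

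**Other safety domains.** SAP 18.3 (vital signs) has an any-time table on numeric criteria that includes unscheduled visits. SAP 18.6 (ECHO) has one for its numeric Severely Abnormal cut-offs. SAP 18.5 (ECG) tabulates the "overall ECG evaluation of clinical significance at any time of the study including unscheduled visits", and separately says "A shift table by visits will also be constructed".

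**Protocol.** Clinic visits are 6-monthly, ±30 days (Table 1). Abnormal tests may be repeated at unscheduled visits (Table 1 footnote 5; Section 8, Unscheduled visits). Section 8.2.2 requires a repeat to confirm a 30% creatinine rise. Section 8.2.3 requires weekly or twice-weekly liver tests after a liver criterion is met. It also requires weekly tests in subjects whose ALT has fallen from 5–8xULN to 3–5xULN and who may stay on drug.

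**The concern.** Long-term safety is the primary objective. The lab values that best describe a liver or renal signal are its peak and its confirmation, and the protocol obtains these mainly at repeats between scheduled visits. The visible SAP leaves those repeats out of the lab shift tables and the by-visit lab summaries. The remaining route into a lab summary table is the investigator's opinion, not a number.

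At stake is a simple question that a safety reader will ask: how many subjects reached ALT ≥3, ≥5 or ≥8xULN, or a 30% rise in creatinine, at any time? As the plan stands, answering it means working through listings.

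**Working it through.** The plan states no figure on this point, so there is none to reproduce. The check compares the data-inclusion rules and adds short arithmetic.

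**1. Which rule governs the lab shift table.** SAP 18 limits outputs to nominal visits and exempts only tables of clinically significant results. A Low/Normal/High shift is not such a table. The reference in 18.4.1 to any post-baseline visit could mean each visit in turn, or the worst value at any time. The ECG shift is explicitly by visit, so different wording for labs may be deliberate. Even on the any-time reading, SAP 18 would still confine the table to nominal visits, because no exception is stated. Baseline is treated differently: SAP 7.2 accepts unscheduled pre-dose values.

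**2. Where the repeats fall.** Six months = 6 × 365.25/12 = 182.6 days. With ±30-day windows, two consecutive post-baseline visits are at least 182.6 − 2 × 30 = 122.6 days (17.5 weeks) apart. For a subject continuing on drug after a finding at a nominal visit, the four panels of the 4-week weekly monitoring in Protocol 8.2.3 take 28 days. All four precede the next nominal visit, so none enters the shift table. A withdrawn subject has an End of Study visit about 30 days after last treatment, which may add one nominal value.

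**3. Where each kind of value can appear.**

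| Finding | Lab shift and by-visit tables | Other summary tables | Listings |
|---|---|---|---|
| ALT above ULN at a nominal visit | Yes: High, and in the by-visit maximum | If judged clinically significant | Yes |
| Higher ALT at a weekly repeat, subject stays on drug | No | Only if judged clinically significant | Yes |
| Liver stopping criterion met at a repeat | No | Yes: adverse event table (serious if Hy's Law) or disposition, not by threshold | Yes |
| Creatinine up 30% at a nominal visit, not confirmed | Yes, but High only if above ULN; also in change from baseline | Only if judged clinically significant | Yes |
| Creatinine rise seen only at a repeat | No | If judged clinically significant, or if drug is stopped | Yes |

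The adverse event route rests on Protocol 7.6 (a lab abnormality leading to interruption or discontinuation) and 8.2.12.4 (clinically significant abnormalities). Protocol 8.2.5 narrows it for findings tied to the underlying disease, unless more severe than expected.

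**4. What the three categories cannot show.** High merges ALT just above ULN with ALT ≥8xULN. A 30% creatinine rise stays Normal when baseline is below 1/1.3 = 76.9% of ULN. Rise needed to reach ULN from a baseline of:
- 50% of ULN: 1/0.5 − 1 = 100%
- 60% of ULN: 1/0.6 − 1 = 67%
- 70% of ULN: 1/0.7 − 1 = 43%

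A worst-value shift alone does not cure this; a threshold count does.

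**5. Numeric any-time tables by domain.** Eight stopping criteria have numeric thresholds: creatinine, ejection fraction and eGFR in Protocol 8.2.2, and five liver criteria in 8.2.3. Seven rest on labs, although five of those seven are built on ALT. One rests on ECHO and none on vital signs. Any-time tables on numeric criteria in the visible SAP: vital signs one (seven criteria), ECHO one, labs none. eGFR is not rescued by the efficacy section, because SAP 17.1 also excludes unscheduled and early-termination visits.

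**6. Illustration with assumed durations.** Let onset be uniform between visits 182.6 days apart. An abnormality lasting D days is present at a nominal visit with probability D/182.6: 8% for 14 days, 15% for 28, 31% for 56 and 46% for 84. This shows how little a nominal-only table sees of a short event. It says nothing about how often such events occur.

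**The case against.** The strongest reply is that serious cases do not disappear. Subjects who meet a criterion in Protocol 8.2.2 must stop drug, and liver criteria 1–5 require product to be withdrawn. Protocol 7.6 then makes the abnormality an adverse event, with no exemption for underlying disease. SAP 18.1.2 tabulates events leading to discontinuation, Hy's Law cases must be reported as serious, and SAP 10 counts withdrawals for stopping criteria. This stands. A reader might infer that liver or renal stopping events could go unreported in summary tables; the documents do not support that. They do leave such cases without a threshold label: the disposition category does not say which criterion was met.

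A reader might also infer that the table of clinically significant labs omits unscheduled visits. It does not: SAP 7.3 and SAP 18 both include them.

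Further points stand in part. Nominal-visit creatinine changes below ULN show in change from baseline, and eGFR is summarised by two equations, but neither counts 30% rises. The first-value rule works both ways, since it also keeps an abnormal first result that a retest does not confirm. The vital signs and ECHO tables do not count protocol stopping thresholds either (ECHO uses severity cut-offs, not the 25% fall in ejection fraction), and ECG is handled like labs. The comparison therefore shows only that the SAP already uses numeric any-time tables elsewhere.

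Finally, SAP 9 defers table format and content to templates that were not available. A threshold table described only there cannot be ruled out.

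**Conclusion.** The point holds as a gap in tabulation. Under the stated rules, lab values from between visits are outside the lab shift tables and by-visit summaries, and they reach a lab summary table only on the investigator's judgement. The real loss is confined to four things: ALT rises in subjects continuing on drug; creatinine rises that are unconfirmed or seen only at a repeat; numeric peaks; and the absence from the visible SAP of a count against the protocol's own lab thresholds.

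One might go further and say that no follow-up panel can ever enter a nominal table. That is safe only for subjects who stay on drug, because the End of Study visit may supply a value for those withdrawn.

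Size: four of four weekly panels fall outside the shift table for a subject continuing on drug. The number of subjects affected cannot be estimated from the documents; with up to 100 enrolled (Protocol 6.1), each is 1/100, about one percentage point. The conclusion assumes that SAP 18 applies as written to 18.4.1 and that the templates add no such table. Weight: minor to moderate, since every value is listed and serious cases surface elsewhere.

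**What to change.** 1. **SAP 18.4.1.** Keep the by-visit tables. Add a shift from baseline to the worst post-baseline value (highest for High, lowest for Low) over all assessments, including unscheduled, retest and early-termination values. State that this is an exception to SAP 18, and define what any post-baseline visit means.

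2. **SAP 18.4.** Add one any-time count table, in the style of the vital signs table in 18.3. Use thresholds already in the protocol as reporting cut-offs only:
   - ALT ≥3, ≥5 and ≥8xULN
   - AST ≥3xULN
   - bilirubin ≥2xULN
   - ALT ≥3xULN together with bilirubin ≥2xULN
   - creatinine ≥30% above baseline, both any occurrence and confirmed on repeat
   - eGFR <30 mL/min/1.73m²

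No change is needed for the table of clinically significant labs.

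The cost is a few sentences of SAP text, one shift table and one count table. No new data are needed and no clinical rule changes. The drawback is that subjects tested more often have more chances to show an abnormal value, so both tables should be read beside the by-visit ones.

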18.1. ADVERSE EVENTS

Adverse Events (AEs) will be coded using Medical Dictionary for Regulatory Activities (MedDRA) central coding dictionary, Version 16.1 and will be summarized. The AE will be presented in summary tables for each of the following items, by the counts and percentages of subjects and events:

- The counts and percentages of subjects and events with each adverse event by SOC and preferred term
- The counts and percentages of subjects and events with each (investigator determined) treatment related adverse event by SOC and preferred term
- The counts and percentages of subjects and events with each adverse event leading to discontinuation of study medication by SOC and preferred term
- The counts and percentage of subjects and events with each serious adverse event by SOC and preferred term
- The counts and percentage of subjects and events with each adverse event leading to death
- Possible Suicidality Related Adverse Event (PSRAE)

Adverse events will also be summarized by the following categories:

- Severity
- Relationship to Study Drug

An overall summary of number of subjects and the events within each of the categories described in the sub-section

Document: \\quintiles.net\enterprise\Sites\CAMTL\IntProjects\SasData\Amicus\AT1001\AXA23225A\Biostatistics\Documentation\SAP\DR\Amicus_AT1001-042_SAP_Final_v1.0_20190821.docx

Author: Amicus

Version Number: Final v1.0

Version Date: 21AUG2019

Template No.: CS_TP_BS016 Revision 5

Reference: CS_WI_BS005

Effective Date: 01Apr2018

below, will be provided as specified in the templates.

A listing including all AEs will be provided. Separate listings for AEs Leading to Discontinuation of Study Medication, Serious AEs, AEs Leading to Death, and PSRAE will also be provided.

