Fabry disease is a rare X-linked lysosomal storage disease caused by mutations of the *GLA* gene, resulting in reduced or absent levels of the lysosomal enzyme α -galactosidase A (α -Gal A). Reduced enzyme activity results in accumulation of the natural substrate globotriaosylceramide (GL-3) in tissues, giving rise to the disease symptoms and ultimately premature death due to renal failure, cardiac disease, and stroke. Current treatment for Fabry disease is enzyme replacement therapy (ERT) which is administered by intravenous infusion every two weeks.

Migalastat hydrochloride (HCl) is an orally administered small molecule that has widespread tissue distribution and is being developed for the treatment of patients with Fabry disease. Migalastat HCl is a pharmacological chaperone and as such stabilizes endogenous α -Gal A allowing it to be properly trafficked to the lysosome where it can degrade GL-3.

The purpose of this study is to investigate the long-term safety and explore the efficacy/pharmacodynamics of migalastat HCl administered 150 mg (equivalent to 123 mg migalastat) every other day (QOD). Subjects enrolled in this clinical protocol will have completed treatment in a previous study of migalastat HCl. **In Japan, subjects enrolled in this clinical protocol will have completed AT1001-012.**

Objective(s)

Primary Objective:

To assess long-term safety of migalastat HCl in the treatment of subjects with Fabry disease who completed treatment in a previous study of migalastat HCl.

Secondary Objective:

To explore long-term efficacy/pharmacodynamics of migalastat HCl in subjects with Fabry disease who have completed treatment in a previous study of migalastat HCl.

Study Design

This is an open-label, non-comparative, long-term extension study for subjects with Fabry disease who have completed treatment in a previous trial of migalastat HCl given as monotherapy. Subjects will enter this extension study immediately upon completion of their final treatment visit in a previous migalastat HCl study. The planned duration of the treatment will vary among subjects and will continue until the date of regulatory approval or marketing authorization and/or commercialization in the participating subject's country, or study termination by the Sponsor, Amicus Therapeutics (Amicus). There will be continuous monitoring of safety data and use of specific stopping criteria for discontinuation of individual subjects who show evidence of clinical deterioration.

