6.4. Withdrawal Criteria

Subjects may discontinue migalastat HCl and withdraw from the study for any reason including, but not limited to, the following:

- At their own request or at the request of their parent or guardian (if the subject is a minor) or legally authorized representative*.
- If, in the investigator's opinion, continuation in the study would be detrimental to the subject's well-being.
- Occurrence of an intolerable adverse event (AE) as determined by the investigator and/or the subject.
- Subject initiates or plans to initiate regular ERT for Fabry disease.
- Suspected hepatotoxicity, as defined by increase of ALT or AST $\geq 3X$ upper limit of normal (ULN) and total bilirubin $> 2X$ ULN when no other reason can be found to explain the increase in liver enzymes.
- Persistent noncompliance with study requirements, such as failure to return to the study site for scheduled visits.
- Pregnancy and/or breast feeding.
- Documented eGFR_{MDRD} value meeting the criteria defined below:
 - An eGFR value (calculated centrally) that is < 30 mL/min/1.73m²

In all cases, the reason for withdrawal and the date of withdrawal must be recorded in the electronic case report form (eCRF) and in the subject's medical records.

* “Legally authorized representative” means an individual or judicial or other body authorized under applicable law to consent on behalf of a prospective subject to the subject's participation in the procedure(s) involved in the research.

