- ⁷ Study Treatment Supply for Study AT1001-042 is intended to occur on Baseline (Visit 1) or in subsequent days within the allowable window for this visit.
- ⁸ Subjects will receive a telephone contact, or contact using another acceptable method, approximately midway between visits to assess Adverse Events and dosing compliance. It is better to have the phone contact performed earlier or later than scheduled, rather than not at all.

Baseline

During transition from the previous study into the current study, the intent is for treatment with migalastat HCl to continue without a break.

Assessments collected as a part of the last treatment visit in the previous study, that are also required for the Baseline Visit in the current study, will serve as the assessment for the Baseline Visit. The visit window for the last treatment visit in the previous study will apply to those Baseline Visit assessments. However, to provide flexibility to investigators and subjects, any Baseline Visit assessment that is required for the current study and not a required assessment for the last treatment visit in the previous study, may be performed up to 30 days after entry into the current study.

Unscheduled visits

Unscheduled visits can be performed at any time point at the investigator's discretion for medical reasons, such as evaluation of AEs and/or repeat laboratory tests.

Early Withdrawal

Subjects who meet any of the withdrawal criteria in Section 6.4 and withdraw from the study will be asked to return for a visit approximately 30 days after last treatment and have end of study assessments performed as shown in Table 1. An echocardiogram (ECHO) will be performed for subjects who have not had an ECHO within the previous 6 months.

End of Study

An End of Study visit will occur within approximately 30 days of the subject's last treatment dose.

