8.2.10. Time Period and Frequency of Detecting AEs and SAEs

The investigator or site staff is responsible for detecting, documenting, and reporting events that meet the definition of an AE or SAE.

AEs will be collected from the start of the subject's first dose of study medication in the current study and until the follow up contact or 30 days after last dose, whichever comes first.

SAEs will be collected over the same time period as stated above for AEs. However, any SAEs assessed **as related** to study participation (e.g., study treatment, protocol-mandated procedures, invasive tests, or change in existing therapy), will be recorded from the time a subject consents to participate in the study up to and including any follow up contact. All SAEs will be reported to Amicus within 24 hours, as indicated in Section [8.2.11](#).

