10.3.4. Key Elements of Analysis Plan

10.3.4.1. Safety Analyses

Exposure

The number of subjects exposed to IP will be summarized. Duration of exposure will also be summarized. Subject exposure will be categorized and the number and percentage of subjects in each category will be presented.

Adverse events

Adverse events will be coded using the MedDRA coding dictionary to collapse similar investigator terms for the adverse events. The various coded (preferred) terms will then be grouped into system organ class (SOC) categories.

The following will be summarized separately for the Treatment Phase and Follow-up Phase, as well as across all study phases combined:

- The percentage of subjects with each adverse event by SOC and preferred term.
- The percentage of subjects with each (investigator determined) treatment-related adverse event by SOC and preferred term.
- The percentage of subjects with each adverse event leading to study withdrawal by SOC and preferred term.
- The percentage of subjects with each serious adverse event by SOC and preferred term.

Other Safety Assessments

For all other safety variables (as listed below), continuous variables will be summarized with descriptive statistics (n, mean, median, standard deviation, minimum, and maximum) and categorical variables will be summarized with frequency distributions.

Vital Signs and Weight

Vital signs (blood pressure and heart rate) and weight data will be summarized by visit. This will include a summary of changes from the Baseline Visit (Visit 1) of this study.

Baseline refers to values from the last treatment visit of the previous migalastat HCl study.

Labs

Laboratory data will be summarized by visit. This will include a summary of changes from the Baseline Visit (Visit1).

ECG

Electrocardiogram results will be assessed at each study visit and will be summarized descriptively over time in box-plots, where relevant, and in tables summarizing the distributions in each group, by study visit.

Further details will be provided in the Statistical Analysis Plan (SAP).

Protocol Deviations

A table will summarize the number and percent of subjects who experienced any protocol deviation. A by-subject listing will also be presented.

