APPENDIX 1. PROGRAMMING CONVENTIONS FOR OUTPUTS

DATES & TIMES

Depending on data available, dates and times will take the ISO8601 form yyyy-mm-ddThh:mm:ss.

SPELLING FORMAT

English US.

PRESENTATION OF TREATMENT GROUPS

In this OLE study, there will be only one treatment administered, e.g. investigational product AT1001, therefore, all summary tables and figures will present the treatment group as “AT1001”.

PRESENTATION OF VISITS

For outputs of ITT population, visits will be represented as follows and in that order:

Long Name (default)
Baseline (V1)
6 Months (V2)
12 Months (V3)
...
End of Study

Unscheduled visits will be in a form of “Unscheduled Visit x.y”, where x refers to the closest previous scheduled visit, and y is an increasing two-digit sequence number starting from 01 to 99 with a step of 1 chronologically.

For subjects re-enrolled under addendum 1.1.2, the visits are planned with a 3-month interval, followed by follow-up visits one month after. It can be presented as n Months (VxA) and n+1 Months FU A, where n refers to 3, 6, 9,

Document: \\quintiles.net\enterprise\Sites\CAMTL\IntProjects\SasData\Amicus\AT1001\AXA23225A\Biostatistics\Documentation\SAP\DR\Amicus_AT1001-042_SAP_Final_v1.0_20190821.docx

Author: Amicus

Version Number: Final v1.0

Version Date: 21AUG2019

Template No.: CS_TP_BS016 Revision 5

Reference: CS_WI_BS005

Effective Date: 01Apr2018

..., e.g. 9 Months FU Addendum, and x refers to the chronological visit number. The baseline and end of study visit are presented as “Baseline (V1A)” and “End of Study (A)”, respectively.

SCHEDULE OF PHARMACOKINETIC ASSESSMENTS FOR ADDENDUM SUBJECT

Pre-dose	Hours Post Dose														
	0	1	2	3	4	6	8	12	24	48	72	96	120	144	168
Baseline assessments (Q4D regimen)															
X	X	X	X	X	X	X	X	X	X		X ¹				
Sample Follow-up Assessments Based on Regimen															
Regimen															
QOD										X					
Q3D										X	X ¹				
Q5D										X			X ¹		
Q6D										X				X ¹	
Q7D										X					X ¹

QOD = every other day; Q3D = every third day; Q4D = every fourth day; Q5D = every fifth day; Q6D = every sixth day; Q7dD = every seventh day

1. Trough sample, to be collected just prior to the next scheduled migalastat administration

SCHEDULE OF BASELINE URINE COLLECTION FOR ADDENDUM SUBJECT

Pre-dose	Hours Post Dose						
0	0-4	4-8	8-12	12-24	24-48 ¹	48-72 ¹	72-96 ¹
X	X	X	X	X	X	X	X

1. Total urine volumes will be collected on these days, if possible.

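### Protocol 10.3.4.1 requires adverse events summarised for the Treatment Phase, the Follow-up Phase and both combined; the SAP text provides only the combined set

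*SAP*

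**What the plan says.** Protocol 10.3.4.1 introduces four AE summaries (all AEs, treatment-related AEs, AEs leading to study withdrawal, serious AEs) with this instruction: "The following will be summarized separately for the Treatment Phase and Follow-up Phase, as well as across all study phases combined".

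SAP 18.1 introduces its own list differently: "The AE will be presented in summary tables for each of the following items, by the counts and percentages of subjects and events". The list covers all AEs, related AEs, AEs leading to discontinuation of study medication, serious AEs, AEs leading to death and suicidality-related AEs. Section 18.1.1 adds ten tables, and 18.1.2 to 18.1.6 describe the individual categories. None mentions a phase, a last-dose cut-off or an on-treatment flag. SAP Appendix 1 adds that, because only one treatment is given, "all summary tables and figures will present the treatment group as" AT1001.

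On timing, Protocol 8.2.10 collects AEs from the first dose in this study "until the follow up contact or 30 days after last dose, whichever comes first". Under Early Withdrawal in Protocol section 8, subjects who withdraw "will be asked to return for a visit approximately 30 days after last treatment". SAP 15 measures exposure from first to last dose only.

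**The concern.** Long-term safety is the primary objective, and AEs head the list of safety assessments in Protocol 8.2.1. The phase split is the protocol's own means of separating what happened on migalastat from what happened after it. Without it, an event three weeks after the last capsule is counted in the same cell as an event in the middle of treatment.

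The post-treatment window is also mixed. One listed reason for leaving is "Subject initiates or plans to initiate regular ERT for Fabry disease" (Protocol 6.4), and Protocol 7.7 requires discontinuation once routine ERT has begun. Other subjects leave because migalastat is approved or marketed locally, or may continue it through another programme (Protocol 5.1). Events in the window may therefore arise on no therapy, on ERT or on migalastat from another source, all reported under AT1001. SAP 18.1.1.2 also treats an AE with missing relationship as potentially related, with no distinction for onset after treatment.

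**Working it through.** The documents state no figure on this point, so there is none to reproduce. The check compares the two texts and then sizes the window.

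**1. Required against supplied.**

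| Category (Protocol 10.3.4.1) | Treatment Phase | Follow-up Phase | Combined |
|---|---|---|---|
| All AEs | not in SAP text | not in SAP text | SAP 18.1, 18.1.1 |
| Treatment-related AEs | not in SAP text | not in SAP text | SAP 18.1 |
| AEs leading to study withdrawal | not in SAP text | not in SAP text | nearest is AEs leading to permanent discontinuation of study medication, SAP 18.1, 18.1.2 |
| Serious AEs | not in SAP text | not in SAP text | SAP 18.1, 18.1.1, 18.1.3 |

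Four categories × three sets = 12 summaries required. The SAP text supplies 4, one through a near equivalent.

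**2. Two time bases.** The AE period ends at the follow-up contact or 30 days after the last dose, whichever is earlier; related serious AEs run up to and including any follow-up contact. The exposure period ends at the last dose. The AE tables can thus cover up to 30 more days per subject than the exposure table.

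**3. Share of AE observation time after the last dose.** Formula: 30 / (exposure days + 30), with exposure days = months × 365.25/12 as in SAP 15. The 30 days is the maximum for AEs in general.

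| Exposure (months) | Exposure (days) | Share |
|---|---|---|
| 6 | 182.6 | 30/212.6 = 14.1% |
| 12 | 365.25 | 30/395.25 = 7.6% |
| 24 | 730.5 | 30/760.5 = 3.9% |
| 36 | 1,095.75 | 30/1,125.75 = 2.7% |
| 48 | 1,461 | 30/1,491 = 2.0% |

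**4. Ceiling across the study.** Protocol 6.1 expects up to 100 subjects: 100 × 30 / 365.25 = 8.2 person-years after the last study dose. This is a ceiling on post-treatment time, not an estimate of time without migalastat.

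**5. Events in the window (illustration).** The documents give no AE rate. Assuming a constant rate of 0.5 to 4 AEs per subject-year, the chance of at least one AE in 30 days is 1 − exp(−rate × 30/365.25), which is 4% to 28%.

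**6. ERT in the window.** The Protocol Summary describes ERT as "administered by intravenous infusion every two weeks". A first infusion on day 1 or 2 after the last capsule puts three in the window (for example days 1, 15, 29); a first infusion on day 7 or 14 puts two (days 7, 21 or 14, 28). Because Protocol 7.7 stops migalastat after routine ERT has started, some ERT may also precede the last study dose.

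**7. Where to cut.** Neither document dates the two phases. With one active capsule every other day (Protocol 7.2), the day after the last capsule is still inside an ordinary dosing interval. A rule that calls everything after the last-dose date follow-up would move that day out of treatment.

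**The case against.** The strongest reply has four parts.

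- **The combined table is required.** A reader might infer that counting post-treatment events under AT1001 is itself an error. It is not: Protocol 10.3.4.1 also asks for all phases combined. This stands. The fault is the two missing sets.
- **Post-treatment is not the same as off drug.** A reader might take the 8.2 person-years as time without migalastat. Protocol 5.1 ends participation on local approval or commercialisation and allows continued supply through other programmes, so some subjects may not stop at all. In addition, 100 is an expected maximum, and collection can end before day 30. This stands.
- **Late events can be found in listings.** A reader might infer that late events cannot be told apart at all. The SAP plans listings of all AEs, study drug administration and all medications, with study day counted from first dose. Late events can be identified by matching these subject by subject. This stands as to identification, but it does not replace the required summaries.
- **The templates may show the split.** SAP 9 and 18.1 refer to templates that were not available. This limits certainty. Nothing in the SAP text, however, calls for a split or defines the phases that one would need.

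It is also true that no hypothesis is tested, so no formal inference changes.

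**Conclusion.** The discrepancy holds. On its text, the SAP omits two of the three sets of AE summaries that the protocol requires for its primary objective, and gives no reason. The remaining set covers a longer period than the exposure table.

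The size is modest for long exposure and larger for early leavers: at most 30 days per subject, which is 14.1% of AE observation time after 6 months, 7.6% after 12 and 2.0% after 48. These shares assume that the full 30 days is observed.

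A reader might go further and conclude that ERT reactions contaminate the migalastat safety profile, or that a primary safety outcome is biased. The documents do not support either. The ERT overlap is possible under Protocol 6.4, 7.7 and 8.2.10, but no number of subjects is given; and safety is the primary objective, with no single safety outcome named. The point is a protocol-SAP reconciliation that should be made because it concerns the primary objective and is cheap.

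**What to change.** In SAP 18.1:

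- Keep the combined tables. Add Treatment Phase and Follow-up Phase tables for the four categories in Protocol 10.3.4.1.
- Define both phases from the last-dose date on the Study Drug Administration eCRF, already used in SAP 15. State a cut-off that allows for the every-other-day interval, for instance by counting the day after the last capsule as treatment.
- State how events with partial or missing onset dates are assigned to a phase.
- Flag events in either phase with onset after a recorded start of ERT, and follow-up events with onset after a recorded start of non-study migalastat. A flag limited to follow-up would miss ERT begun before the last study dose.
- If the sponsor prefers to report only the combined set, record the departure from the protocol and the reason.

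The split itself uses last-dose and AE onset dates and needs no change in conduct. The flags work only where the start of the other therapy was recorded. The cost is SAP wording, eight more summaries (four categories × two phases) and the partial-date rule. Follow-up tables may be sparse.
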